22.6 Monitoring, Audits and Inspections

During the investigation, the monitor will have regular contacts with the investigative site. These contacts will include visits to confirm that the facilities remain adequate to specified standards and that the investigative team is carrying out the procedure stated in the investigational plan. All data must be accurately recorded in the Case Report Forms. Source data verification (a comparison of data in the CRF with the subject's medical records and other records at the investigation site) with access to records will also be performed. The monitor or other sponsor personnel will be available between visits if the Investigator or other staff at the site needs information and/or advice. Authorized representatives of the study sponsor, and FDA, may visit the site to perform audits / inspections, including source data verification.

22.7 Investigator Access to the Data and Publication Policies

At the conclusion of the trial, a multi-center abstract reporting the primary results will be prepared and presented at a major medical meeting. A multi-center publication will also be prepared for publication in a reputable medical journal. The publication of results from any single center experience within the trial will not be allowed until the aggregate study results have been published, unless there is written consent from the study sponsor. The analysis of other pre-specified and non-pre-specified endpoints will be performed by the sponsor. Such analyses as well as other proposed investigations will require the approval of the Operations Committee. It is anticipated that many secondary manuscripts with principal authorship drawn from members of the Steering Committee. For purposes of timely abstract presentation and publication, such secondary publications will be delegated to the appropriate principal authors, and final analyses and manuscript review for all multi-center data will require the approval of the Operations Committee.

23.0 ADDITIONAL STUDY AND ADMINISTRATIVE ELEMENTS

23.1 Duration of Investigation

It is anticipated that some of the study participants will take part in this clinical study for up to 7 years. Given an accrual rate of approximately 15 patients per month, it is anticipated that time for recruitment will be 12 months for the enrollment of 183 study participants to yield an estimated final completed study group total of 147 study participants.

23.2 Participant Accountability

23.2.1 Missed Follow-up Visits

Study participants that miss a scheduled visit will be contacted to reschedule as soon as possible. Study participants failing to return for follow-up, or failing to return to contact attempts by site staff for follow-up visits, shall be contacted a minimum of three times by the Study Coordinator or Investigator, with the last attempt by certified mail, before exiting the study participant as lost to follow-up.

23.2.2 Participant Withdrawal

Study participants will be advised that they may voluntarily withdraw from the study at any time and they will be instructed to notify the Investigator immediately, should they choose to withdraw. Study participants may withdraw for any reason and are not obligated to reveal their reasons for withdrawal.

23.3 Documentation Requirements

All study information beginning at the screening assessment continuing through the final follow-up will be recorded on source documents such as initial history and physical noting eligibility, outside medical records, written records of all research procedures, including questionnaires, diaries, follow-up documentation, lab work, pathology reports, ECGs, X-ray reports, and any other diagnostic information, record of medications dispensed or devices used, clinic charts or hospital records. Data will be transcribed onto participant case report forms (CRFs) or recorded on eCRFs (electronic CRFs) in a database supplied by the sponsor.

23.4 Study Monitoring

Monitoring of the study will be conducted by the sponsor or its designee following 21CFR 50, 54, 56, and 812 and the guidelines established by the Declaration of Helsinki and ICH GCP (to the extent that they are consistent with U.S. federal regulations). A site initiation meeting will be held and periodic site visits will be performed. The monitor will maintain oral and written communications with the Investigators and study personnel. Case report forms will be reviewed with source records and compliance with the protocol will be documented.

23.5 Data Management

Study data will be maintained in a password-protected electronic database created by the Sponsor specifically for this research study. Study participants will be identified only by an anonymous study identification number.

23.6 Registration of the Clinical Trial

The clinical trial will be registered and maintained on the publicly available clinical trials website (www.clinicaltrials.gov) by the study sponsor within 21 days of the first study enrollment.

23.7 Amendments to the Clinical Investigational Plan

Any change to the approved investigational plan must be documented in a written and numbered CIP amendment with a justification for the amendment. Changes to the investigational plan will only be effected following IRB and FDA approval as applicable.

23.8 Device Accountability

All of the valves and valve delivery catheters used in the study will be maintained in a secure location at the investigational site until used or returned to the sponsor. Study devices will only be used under the Investigator's supervision in study participants. The Investigator will not supply the study device to any person not authorized under this protocol to receive it. The Investigator shall maintain accurate device accounting records including quantity and date of receipt, person in receipt, lot number, use or disposition,

participant identification associated with device, date of expiration (if applicable) and quantity and date of any devices returned to the Sponsor.

23.9 Deviations from the Clinical Investigation Plan

Except in an emergency, prior approval by the study Sponsor is required for changes in or deviations from the investigational plan. If the changes or deviations may affect the scientific soundness of the study or the rights, safety, or welfare of participants, FDA and IRB approval is required. Every effort should be made to comply with the requirements of the protocol. Deviations will be recorded with an explanation for the change. The study Sponsor is responsible for analyzing the deviations and assessing their significance. Corrective action will be implemented to avoid repeat deviations.

24.0 INVESTIGATOR RESPONSIBILITIES

The Investigator is responsible for ensuring that this investigation is conducted according to all signed agreements, the study protocol, and the applicable code of Federal Regulations. This section describes these responsibilities at his/her site.

24.1 Study Administration

The Investigator must read and acknowledge his/her understanding of the study protocol and ensure adequate training of staff for executing the study has occurred. Specifically, he/she must: Sign the Protocol Signature Page, Clinical Trial Agreement, Non-Disclosure Agreement and Financial Disclosure and provide a copy of each to the Pulmonx Clinical Research Department or designee.

- Provide current copies of each Investigator's, Sub-Investigator's, and Coordinator's Curriculum Vitae (CV) to the Pulmonx Clinical Research Department.
- Provide current copies of each Investigator's, and Sub-Investigator's Medical License as required throughout the course of the study.
- Provide documentation of GCP training for all study staff.
- Complete training using the Pulmonx Chartis Assessment System prior to treating enrolled subjects.
- Complete training using the Pulmonx Endobronchial Valve System prior to treating enrolled subjects.
- Delegate appropriate and qualified staff as indicated on the Site Delegation of Authority Log.
- Complete all required study procedures and documentation at all visits.

24.2 Institutional Review Board (IRB) Approval

The Investigator must submit the study protocol to his/her IRB and obtain their written approval before being allowed to participate in the study. Specific responsibilities include:

- Submit proposed protocol amendments and informed consent revisions to the IRB/IEC and await approval.

- Inform sponsor and IRB of any unanticipated device-related events (UADEs) within 24 hours of knowledge.
- Submit all required reports to IRB/IEC and sponsor within specified timeframes.

24.3 Conduct the Informed Consent Process

Part of the IRB approval must include approval of an Informed Consent Form specific to the study. The Investigator or his/her designee must administer these approved Informed Consent text to each prospective study candidate and obtain the study candidate's signature on the text, prior to conducting any study-specific tests and enrollment into the study, respectively. The study sponsor will provide Sample Informed Consent text for the Informed Consent forms to the Investigator. This text may be modified to suit the requirements of the individual site. A copy of the informed consent form that has been approved by the reviewing IRB will be provided to the study sponsor. Specifically, the Investigator must:

- Explain all study procedures to the study candidates and obtain written informed consent.
- Ensure HIPAA Authorization is obtained from each study participant and on file.

24.4 Study Coordinator

To assure proper execution of the study protocol, each investigator must identify a Study Coordinator for the site. Working with and under the authority of the Investigator, the Study Coordinator assures that all study requirements are fulfilled, and is the contact person at the site for all aspects of study administration.

24.5 Investigator Records

Each Investigator must maintain the following accurate, complete, and current records relating to the conduct of the investigation. The data for some of these reports may be available in computerized form from the sponsor but the final responsibility for maintenance remains with the Investigator. Study-related documents must be retained for a minimum of two years after study completion and access must be permitted to the study sponsor monitor to inspect facilities and records. Specific examples of records maintenance include:

24.5.1 Correspondence

The study site will maintain records of all correspondence with another Investigator, an IRB, a Core Laboratory, the Study Sponsor, a monitor, or FDA, including required reports.

24.5.2 Study Devices

Records of receipt, use, or disposition of the study device, including receipt dates, serial and lot numbers, names of all persons who received or used the device, why and how many devices were returned to the study Sponsor or otherwise disposed of.

24.5.3 Study Participant Records

Records of each study participant's case history, including study-required Case Report Forms, evidence of informed consent, all relevant observations of adverse device effects, the condition of each study participant upon entering and

during the course of the investigation, relevant medical history, the results of all diagnostic testing, and the date of each study treatment.

24.5.4 Protocol and Deviations

The protocol, along with any documentation showing the dates and reasons for any protocol deviations, will be maintained by the study site.

24.5.5 Investigator Reports

The reports for which the Investigator has responsibility to generate are shown in the table below. The table also shows who should be the recipient of the report and timeframe for submitting it. While some of these reports will be developed by or with the assistance of Pulmonx, the final responsibility for them rest with the Investigator.

Type of Report	Prepared by Investigator For:	Time Constraints of Notification
Unanticipated Adverse Effect	Sponsor	As soon as possible but no later than 10 working days after knowledge of the event.
Withdrawal of IRB Approval	Sponsor	Within 5 working days.
Progress Report	Sponsor / IRB	Submitted at least annually.
Protocol Deviations to protect the life or physical well-being of the subject in an emergency	Sponsor / IRB	Within 5 working days.
Informed Consent Not Obtained prior to device use	Sponsor / IRB	Within 5 working days.
Final Summary Report	Sponsor / IRB	Within 3 months of study completion/termination.

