21.2 Serious Adverse Events and Reporting

A serious adverse event (SAE) is any untoward medical occurrence that:

- Results in death,
- Is life-threatening,
- Requires inpatient hospitalization or prolongation of existing hospitalization, or
- Results in persistent or significant disability/incapacity, or congenital

anomaly/birth defect.

All serious adverse events should be reported immediately (within 24 hours of knowledge of the event) to the study sponsor. All IRB and FDA reporting requirements will be followed.

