21.3 Unanticipated Adverse Device Effects (UADE) and Reporting

Unanticipated adverse device effects (UADE) are defined as: Any serious adverse effect on health or safety or any life-threatening problem or death caused by, or associated with the study device, if that effect, problem, or death was not previously identified in nature, severity, or degree of incidence in the investigational plan, Investigator's Brochure, or package insert, or any other unanticipated serious problem associated with a device that relates to the rights, safety, or welfare of subjects. All unanticipated adverse device effects must be reported immediately (within 24 hours of knowledge of the event) to the study Sponsor. The Investigator must submit to the sponsor and to the reviewing IRB a written report as soon as possible, but in no event later than 5 working days after the Investigator first learns of the event.

A sponsor who conducts an evaluation of a UADE under CFR 812.46(b) shall report the results of such evaluation to FDA and to all reviewing IRBs and participating investigators within 10 working days after the sponsor first receives notice of the effect. Thereafter the sponsor shall submit such additional reports concerning the effect as FDA requests.

A sponsor who determines that a UADE presents an unreasonable risk to subjects shall terminate all investigations or parts of investigations presenting that risk as soon as possible. Termination shall occur not later than 5 working days after the sponsor makes this determination and not later than 15 working days after the sponsor first received notice of the effect.

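### The investigator report table allows 10 working days, to the sponsor only, for an unanticipated device effect that two other protocol sections require within 24 hours

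*Protocol*

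**What the plan says.** Three places in the protocol tell the investigator how to report an unanticipated adverse device effect (UADE).

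- **Section 21.3** sets two duties. The first is notice: such an effect "must be reported immediately (within 24 hours of knowledge of the event) to the study Sponsor". The second is a written report to the sponsor and the reviewing IRB, "in no event later than 5 working days after the Investigator first learns of the event".
- **Section 24.2**, among the investigator's IRB duties, reads: "Inform sponsor and IRB of any unanticipated device-related events (UADEs) within 24 hours of knowledge".
- **Section 24.5.5** is a table of investigator reports with recipients and time limits. For an unanticipated adverse effect the only recipient is the sponsor, and the limit is "As soon as possible but no later than 10 working days after knowledge of the event".

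Two sponsor deadlines depend on when the sponsor hears. Section 21.3, repeated in Section 25.6.1, requires the results of the sponsor's evaluation to go to FDA, IRBs and investigators "within 10 working days after the sponsor first receives notice of the effect". If the sponsor finds an unreasonable risk, Section 21.3 requires termination within 5 working days of that determination and "not later than 15 working days after the sponsor first received notice of the effect".

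A parallel route exists in Section 21.2: "All serious adverse events should be reported immediately (within 24 hours of knowledge of the event) to the study sponsor".

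**The concern.** Section 24.5.5 is where a coordinator would look up who must be told and by when. Its rows for withdrawal of IRB approval, device use without consent, and emergency deviations agree with their counterparts in Sections 17.1, 21.4 and 21.5, so a site has reason to trust the table. The row that departs from the body text is the one for unexpected device harm.

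The sponsor's evaluation and outer termination deadlines are counted from its own first notice, so any slack given to the investigator passes through to them. A late notice could mean late review while participants are still exposed. The SAP records 190 enrolled, so main enrolment is past, but Sections 7.5 and 8.7.1 still provide for remaining crossover participants to be treated, Section 12 allows valve replacement and adjustment, and treated participants have adverse events collected through 5 years.

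**Working it through.** The plan offers no calculation here. The check is a comparison of texts, followed by simple addition.

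**Step 1. Inputs, side by side**

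| Source (Protocol) | Duty | Limit | Recipient |
|---|---|---|---|
| 21.3 | Notice of UADE | 24 hours from knowledge | Sponsor |
| 21.3 | Written report of UADE | 5 working days from first learning | Sponsor and IRB |
| 24.2 | Notice of UADE | 24 hours from knowledge | Sponsor and IRB |
| 24.5.5 | Unanticipated adverse effect | 10 working days from knowledge | Sponsor |
| 21.3, 25.6.1 | Sponsor's evaluation report | 10 working days from sponsor's first notice | FDA, IRBs, investigators |
| 21.3 | Termination for unreasonable risk | 5 working days from determination, and no later than 15 from first notice | – |
| 21.2 | Serious adverse event | 24 hours from knowledge | Sponsor |

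**Step 2. Is it the same report?** The table row does not use the term UADE, but the protocol defines no other report of an unanticipated effect. I take them to be the same.

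**Step 3. Can either reading of the row be squared with the text?**

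- Read as the *first notice*, which the column heading about notification supports: 10 working days against 24 hours. Counting 24 hours as about 1 working day, the excess is 10 − 1 = about 9 working days.
- Read as the *written report*, which the table's introduction supports by speaking of reports to be generated and submitted: 10 against 5 working days, an excess of 10 − 5 = 5.
- On either reading the IRB is missing. Section 21.3 names it for the written report, and Section 24.2 for the 24-hour notice.

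Sections 21.3 and 24.2 also differ from each other: only 24.2 puts the IRB on the 24-hour notice.

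**Step 4. Effect on the sponsor's clocks.** Latest date, in working days after site knowledge = investigator's notice limit + sponsor's limit.

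| | 24-hour notice | Row as first notice | Difference |
|---|---|---|---|
| Evaluation report | 1 + 10 = about 11 | 10 + 10 = 20 | about 9 |
| Outer termination limit | 1 + 15 = about 16 | 10 + 15 = 25 | about 9 |

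The right-hand figures need two conditions: the site uses the row for its first notice, and no earlier report has given the sponsor notice. If the row is only the written report, the 24-hour notice still starts the clocks and the difference in this table is zero.

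The termination line is an outer limit. The limit of 5 working days after the sponsor's determination also applies and may bind sooner.

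**The case against.** The best case against giving this weight concerns the consequence. The UADE definition in Section 21.3 mainly covers serious effects, life-threatening problems and deaths. Most of these will also be serious adverse events, which Section 21.2 separately sends to the sponsor within 24 hours. Such a report would ordinarily count as the sponsor's first notice. To reach 20 or 25 working days, a site would have to miss the 24-hour rules in Sections 21.3 and 24.2 and, for most events, the one in 21.2 as well. Section 25.2 also commits the sponsor to prompt evaluation once it knows.

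This stands, and it limits the claim. A reader might infer that the table does delay the sponsor's safety review, or that 20 and 25 working days are the plan's effective limits. The documents do not support that: the table permits a delay under one of two plausible readings, and other rules would usually prevent it. Nor is there any sign that 10 working days was chosen deliberately over 24 hours; it reads as a clerical inconsistency.

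The objection does not remove the conflict. Section 21.2 sets no 24-hour notice to the IRB. The UADE definition also reaches other unanticipated serious problems bearing on participants' rights, safety or welfare, which need not meet the serious adverse event definition.

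**Conclusion.** The point holds as an internal contradiction in an operative safety-reporting rule. The Section 24.5.5 row cannot be reconciled with Sections 21.3 and 24.2 on any reading of time limit or recipient. The size depends on the reading in Step 3: a permitted late start of up to about 9 working days for the sponsor's clocks in one case, and in the other a written report permitted 5 working days past its cap with the clocks unaffected. The first figure rests on counting 24 hours as about one working day and on no serious adverse event report arriving first. Nothing in the documents shows that a site has used the row in this way.

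Exposure to new implants is narrower than during main enrolment, but it has not ended. The matter is confined to safety reporting, so its priority is modest: it should be corrected, but it has no bearing on the effectiveness conclusions.

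**What to change.** Reconcile Sections 21.3, 24.2 and 24.5.5 so that the protocol states one deadline for the first notice, one for the written report, and one recipient list for each. The two duties should stay distinct, because Section 21.3 separates them; a single merged timeline would lose that. The reconciled text should settle whether the IRB receives the first notice, and the table should use the term UADE and show notice and written report as separate rows.

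Section 23.7 requires a written, numbered amendment with a justification, and IRB and FDA approval as applicable. The cost is therefore an administrative amendment plus a notice telling sites which row has changed. No data collection or analysis changes.

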25.0 SPONSOR RESPONSIBILITIES

25.1 Clinical Site Selection and Training

- Submit the IDE application to FDA and obtain approval from FDA to initiate the study.
- Ensure that IRB approval and continuing review are obtained.
- Select the clinical Investigators and study sites, and other consultants who participate in the study.
- Ensure that the Investigator is an appropriately qualified practitioner legally entitled to practice.
- Ensure that the Investigator is trained and experienced in the field of application of the device under consideration.
- Ensure that the Investigator has sufficient background and meets the requirements for conducting a clinical investigation.
- Ensure that the appropriate information and training are provided to the Investigator in the use of the device to be used in the study in accordance with the clinical investigation plan.

- Obtain from each participating Investigator a signed agreement which includes: 1) Investigator's CV, statement of the investigator's relevant experience and/or information regarding other research activities, including instances where the research activity was terminated.
- Provide financial support to each study site and the core laboratories per individual contracts with each site.
- Provide the study device to participating study sites, in quantities sufficient to support study activities, per agreements executed with the study sites.
- Provide training to Principal Investigator(s) and Study Coordinator(s).

